Visit tolerance interval (days)	-8 to -35		±2	±2	±2	±4	±4	±4	±7	±7	±7	±7	±7	±7	±7	±7	±7	±7	±7
Dispense and weigh (tube with cap) TCS ^f	X	X	X	X	X	X	X	X	X	X	X	X	X	X	X	X	X	X	X
Weigh (tube with cap) and record returned TCS ^f		X	X	X	X	X	X	X	X	X	X	X	X	X	X	X	X	X	X
Scales																			
vIGA-AD	X	X	X	X	X	X	X	X	X	X	X	X	X	X	X	X	X	X	X
EASI	X	X	X	X	X	X	X	X	X	X	X	X	X	X	X	X	X	X	X
SCORAD	X	X	X	X	X	X	X	X	X	X	X	X	X	X	X	X	X	X	X
Health Outcomes Measures and Other Questionnaires																			
POEM ^g	X	X	X	X	X	X	X	X	X	X	X	X	X	X	X	X	X	X	X
CDLQI /IDQOL ^g	X	X	X	X	X	X	X	X	X	X	X	X	X	X	X	X	X	X	X
DFI ^g		X	X	X	X	X	X	X	X	X	X	X	X	X	X	X	X	X	X
PROMIS-Depression ^g	X	X		X	X	X	X	X	X	X	X	X	X	X	X	X	X	X	X
PROMIS-Anxiety ^g	X	X		X	X	X	X	X	X	X	X	X	X	X	X	X	X	X	X
EQ-5D-Y ^g		X	X	X	X	X	X	X	X	X	X	X	X	X	X	X	X	X	X
WPAI-AD-CG ^g		X	X	X	X	X	X	X	X	X	X	X	X	X	X	X	X	X	X
Missed School Days for school age children ^g	X	X	X	X	X	X	X	X											
PRISM ^g	X	X	X	X	X	X	X	X											
Itch NRS ^g	X	X	X	X	X	X	X	X											
Skin Pain NRS ^g	X	X	X	X	X	X	X	X											
ADSS ^g	X	X	X	X	X	X	X	X											
PGI-S-AD ^g	X	X	X	X	X	X	X	X											
TCS Use ^g	X	X	X	X	X	X	X	X											

	Screening	Double-blinded Treatment							Long-term Extension Treatment										
	Period 1	Period 3							Period 4										
Visit number	1	2	3	4	5	6	7	8	9	10	11	12	13	14	15	16	17	18	19
Weeks from randomization	0	1	2	4	8	12	16	20	24	28	40	52	64	76	88	100	112	124	
Visit tolerance interval (days)	-8 to -35		±2	±2	±2	±4	±4	±4	±7	±7	±7	±7	±7	±7	±7	±7	±7	±7	±7
C-SSRS and Self-Harm Supplement ^h	X	X	X	X	X	X	X	X	X	X	X	X	X	X	X	X	X	X	X
Self-Harm Follow-up Form ⁱ	X	X	X	X	X	X	X	X	X	X	X	X	X	X	X	X	X	X	X
Laboratory Assessments																			
Clinical chemistry ^{j, q}	X	X			X	X	X	X	X	X	X	X	X	X	X	X	X	X	X
Hematology ^q	X	X			X	X	X	X	X	X	X	X	X	X	X	X	X	X	X
Lipids (fasting) ^{k, q}		X					X			X		X		X		X		X	
IGF-1 and IGFBP-3 ^q		X					X			X		X		X		X		X	
Left hand x-ray ^l (see Section 9.4.9.3 for ongoing patients)		X					X					X		X		X		X	
X-ray of the knee ^l (see Section 9.4.9.3 for ongoing patients)		X							X			X		X		X		X	
Gonadal hormones (patients 8 to <18 years old) ^{m, q}		X					X			X		X		X		X		X	
Serum Pregnancy ⁿ	X																		
TSH	X																		
HIV	X																		
HCV antibody ^o	X																		
HBV testing	X																		
HBV DNAP	X						X			X	X	X	X	X	X	X	X	X	
Urinalysis ^q	X	X			X	X	X	X	X	X	X	X	X	X	X	X	X	X	
Urine Pregnancy ^{n, q}		X		X	X	X	X	X	X	X	X	X	X	X	X	X	X	X	

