9.1.4.14. Additional Assessments (TCS Use, Missed School Days)

Topical corticosteroids use will be collected using a daily diary. This is a single question used to record if a patient has applied a TCS to the skin in the last 24 hours. Either the patient or parent/caregiver can provide the response.

The number of missed school days for school age children will be reported via daily diary by the parent/caregiver or patient.

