10.3. Statistical Analyses

10.3.1. General Statistical Considerations

Statistical analysis of this study will be the responsibility of Lilly or its designee. A detailed SAP describing the statistical methodologies will be developed by Lilly or its designee.

Any change to the data analysis methods described in the protocol will require an amendment ONLY if it changes a principal feature of the protocol. Any other change to the data analysis methods described in the protocol, and the justification for making the change, will be described in the clinical study report (CSR). Additional exploratory analyses of the data will be conducted as deemed appropriate.

All tests of treatment effects will be conducted at a 2-sided alpha level of 0.05, unless otherwise stated (e.g., refer to Section 10.3.7.3). Treatment comparisons of discrete efficacy variables between baricitinib and placebo will be made using a logistic regression analysis with region, disease severity, age, treatment group, and treatment group-by-age interaction in the model. The percentages, difference in percentages, and 95% confidence interval (CI) of the difference in percentages will be reported. Treatment-by-age interaction will be added to the logistic regression model of the primary and key secondary variables as a sensitivity analysis. If this interaction is significant at a 2-sided 0.1 level, further inspection will be used to assess whether the interaction is quantitative (i.e., the treatment effect is consistent in direction but not size of effect) or qualitative (the treatment is beneficial for some but not all age groups). The p-value from the Fisher exact test will also be produced.

When evaluating continuous measures over time, a restricted maximum likelihood-based mixed-effects model of repeated measures (MMRM) will be used. The model will include treatment, age cohort, baseline severity, visit, and treatment-by-visit interaction, and treatment-by-age cohort interaction as fixed categorical effects and baseline score and baseline score-by-visit interaction as fixed continuous effects. Region may be included in the model if

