10.3.3.2. Secondary Analyses

The following secondary categorical outcomes will be analyzed in a similar manner as the primary, that is, using the same logistic regression model. Nonresponder imputation will be used for these analyses unless otherwise noted.

- EASI75 at Week 16 and 1 year. EASI75 is defined as having an improvement of at least 75% from baseline. Besides NRI, this outcome will also be analyzed using observed cases, that is, whether rescue medication was given or not.
- EASI90 at Week 16. EASI90 is defined as having an improvement of at least 90% from baseline.
- EASI50 at Week 16. EASI50 is defined as having an improvement of at least 50% from baseline.
- SCORAD75 at Week 16 and 1 year. SCORAD75 is defined as having an improvement of at least 75% from baseline.
- SCORAD90 at Week 16. SCORAD90 is defined as having an improvement of at least 90% from baseline.
- IGA score of 0 or 1 (clear or almost clear skin) and ≥ 2 -point improvement from baseline at Week 4 and 1 year.

- IGA of 0 at 16 weeks.
- 4-point improvement in Itch NRS at 1 week, 2 weeks, 4 weeks, and 16 weeks.

The following continuous measures will be analyzed with the MMRM analysis described above unless otherwise noted. Contrasts within the MMRM analysis will be used to assess treatment differences for time points of interest as specified above in the list of objectives.

- Mean change from baseline in the following outcome measures:
 - ADSS Item 2
 - EASI score
 - SCORAD score
 - BSA
 - Itch NRS
 - Skin Pain NRS
 - POEM
 - PGI-S-AD
 - PROMIS-Depression
 - PROMIS-Anxiety
 - DFI
 - CDLQI and IDQOL total score
 - WPAI-AD-CG
 - EQ-5D-Y
 - PRISM

Baricitinib tablet or oral suspension product acceptability and palatability during the PK lead-in period will be summarized categorically (frequency and percentage) by age group, for each visit separately and in aggregate.

The EASI total score and SCORAD total score will also be analyzed as observed, that is, not assuming missing values after rescue medication is given.

The following categorical data will be analyzed using Fisher exact test described above unless otherwise noted.

- Patients requiring rescue with TCS
- Patients requiring rescue with systemic treatments
- School days missed

The following measures will be analyzed by an ANCOVA with treatment and baseline value in the model.

- Mean number of days without use of TCS over 16 weeks
- Mean gram quantity of TCS used over 16 weeks (tube weights)

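### Missed school days is collected as a diary count but assigned to Fisher's exact test as categorical data, a valid but inefficient choice that differs from how the same section treats a like diary count

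*Protocol*

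**What the plan says.** Protocol Section 9.1.4.14 defines the measure as a quantity: "The number of missed school days for school age children will be reported via daily diary by the parent/caregiver or patient". The Schedule of Activities for randomized patients (Table JAIP.2) lists "Missed School Days for school age children" at every visit from screening through Visit 8 (Week 16). Pre-treatment diary data therefore exist, and collection is limited to children of school age.

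Protocol Section 10.3.3.2 then sets the method: "The following categorical data will be analyzed using Fisher exact test described above unless otherwise noted". Three items follow. Two are yes/no (needing rescue with TCS, needing systemic rescue). The third is "School days missed". No dichotomy, bands or counting period are given there. The description that the sentence points back to, in Section 10.3.1, says for discrete efficacy variables only that "The p-value from the Fisher exact test will also be produced", and for safety applies the test to adverse events, discontinuation and similar categories.

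The list directly below in Section 10.3.3.2 begins "The following measures will be analyzed by an ANCOVA with treatment and baseline value in the model" and includes "Mean number of days without use of TCS over 16 weeks".

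**The concern.** The protocol names both a data type (categorical) and a test (Fisher) for a variable that it collects as a number of days. Two diary-based day-counts stand in adjacent lists. One is kept as a quantity and adjusted for baseline; the other is called categorical and gets an unadjusted test. No reason is given for the difference.

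Fisher's test can be applied to a count in two ways. With each value as its own category, it ignores that 5 days is more than 1. After a split into any versus none, a child who missed 1 day counts the same as a child who missed 20. Neither way uses baseline absence or allows for unequal numbers of diary days, for example after early withdrawal. At stake is the chance of seeing an effect on school absence, not the validity of a claim.

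**Working it through.** The protocol states no power, absence rate or effect size for this variable, so there is no figure to reproduce. The check asks how much the named test gives up.

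**Inputs.** From the protocol: two-sided alpha 0.05 (Section 10.3.1) and 110 patients per arm (Section 5.1). Assumed, because the protocol is silent: negative binomial counts with variance m + k·m², k = 1 or 2; control mean m from 0.5 to 8 missed days over 16 weeks; rate ratio 0.5; 80 to 110 school-age patients per arm.

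**Step 1: information kept by any versus none.** For the log mean, one patient's full count carries information m/(1 + k·m). The probability of no missed day is p0 = (1 + k·m)^(−1/k). The any/none indicator carries [m/(1 + k·m)]² × p0/(1 − p0). The share kept is the ratio of the two:

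share = [m/(1 + k·m)] × [p0/(1 − p0)], which for k = 1 reduces to 1/(1 + m).

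Examples:
- k = 1, m = 4: 1/(1 + 4) = 20%.
- k = 2, m = 0.5: p0 = 2^(−1/2) = 0.707; share = 0.25 × 0.707/0.293 = 60%.

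| Control mean (days) | 0.5 | 1 | 2 | 4 | 8 |
|---|---|---|---|---|---|
| Share kept, k = 1 | 67% | 50% | 33% | 20% | 11% |
| Share kept, k = 2 | 60% | 46% | 32% | 22% | 15% |

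More than half is lost once the control mean exceeds about 1 day. Below that the loss is about a third to a half.

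**Step 2: simulated power, any versus none.** 110 per arm, rate ratio 0.5, 1,500 trials per cell. Each cell gives Fisher any/none, then the Wilcoxon rank-sum test on the counts, then a Wald test of the log ratio of means.

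| Control mean (days) | k = 1 | k = 2 |
|---|---|---|
| 0.5 | 58 / 68 / 75% | 43 / 55 / 65% |
| 1 | 66 / 84 / 92% | 47 / 65 / 80% |
| 2 | 66 / 93 / 97% | 43 / 70 / 86% |
| 4 | 53 / 95 / 99% | 36 / 76 / 92% |
| 8 | 39 / 99 / 100% | 28 / 76 / 93% |

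At 80 per arm with k = 1 the pattern is the same: 41 / 52 / 61% at a mean of 0.5 days and 26 / 92 / 97% at 8 days.

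The gap narrows when absence is rare and the effect smaller. At 95 per arm, control mean 0.5 days, k = 2 and a one-third reduction, the rank test has about 21% power and Fisher any/none about 15%.

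**Step 3: Fisher on ungrouped counts.** Using the r × c (Freeman–Halton) form, 110 per arm, k = 1, rate ratio 0.5, 600 trials, power against the rank test was 63% vs 83% at a mean of 1 day, 61% vs 95% at 4 days and 55% vs 97% at 8 days. Relabelling the count values at random left the p-value of one data set unchanged within Monte Carlo error (0.085 vs 0.084), which confirms that this form ignores order.

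**Step 4: the two lists side by side.** Days without TCS and missed school days both come from the daily diary described in Section 9.1.4.14. The first gets ANCOVA with treatment and baseline, the second an unadjusted Fisher test.

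**The case against.** The best defence is that the SAP, which is not shown, may define the derived variable. The sentence carries an exception clause, Section 10.3.1 defers detail to the SAP, and Section 10.3.7.1 says that health outcomes use continuous or categorical methods. If the SAP defines any missed day as the outcome, Fisher's test fits that outcome. This stands in part: a missing cut-point alone would be no finding. But the protocol does not leave the method open, and a dichotomy set later would keep the loss shown above.

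The second defence is that the loss depends on an absence rate that nobody has stated. This stands in full. A reader might infer that Fisher's test throws away most of the information; the documents do not support that, because for absence below about 1 day over 16 weeks any versus none keeps half or more.

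Three other strong readings also fail. A reader might infer that the test is invalid, but Fisher's exact test controls Type I error on either form. A reader might infer that children below school age would dilute the comparison, but collection is already restricted to school-age children. A reader might infer that a trial conclusion is at risk, but missed school days appears in neither the Synopsis objectives nor Table JAIP.3, and is outside the multiplicity-controlled list in Section 10.3.1. Section 9.1.6 also counts it among measures still being developed and validated.

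**Conclusion.** The point holds as a mismatch between data type and method. Section 10.3.3.2 fixes an inefficient test for a count, and is inconsistent with its own handling of days without TCS. Fisher's test had lower power than an analysis of the counts in every scenario run with a true effect. The cost runs from modest (58% vs 68% for the rank test at a control mean of 0.5 days, k = 1) to large (53% vs 95% at 4 days, k = 1). These figures rest on assumed negative binomial counts, a halved rate and 110 school-age patients per arm; the protocol supplies none of the rates, the dispersion or the school-age number. The importance is low: the primary conclusion and all multiplicity-controlled results are unaffected.

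**What to change.** Move missed school days out of the Fisher list in Section 10.3.3.2. Analyse it as a quantity in the school-age patients for whom it is collected, adjusted for baseline absence and for the number of diary days reported. The smallest change is ANCOVA as in the adjacent list, or rank ANCOVA if the counts are skewed. A negative binomial model with log(diary days reported) as offset is an alternative. Keep any versus none with Fisher's test as a supportive summary.

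The change is to wording in the protocol or SAP. The data are already collected, so the cost is a little more analysis work.

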5.1. Overall Design

Study I4V-MC-JAIP (JAIP) is a Phase 3, multicenter, randomized, double-blind, placebo-controlled, parallel-group, outpatient study evaluating the pharmacokinetics, efficacy, and safety of baricitinib compared with placebo in pediatric patients with moderate-to-severe AD. The study is divided into 5 periods, a 5-week Screening period, a 2-week Open-label PK lead-in period, a 16-week Double-Blind Treatment period, an up to 5-year Long-term Extension period, and a 4-week Post-treatment Follow-up period. While the primary objective of this study is to investigate whether baricitinib is superior to placebo in the treatment of the signs and symptoms of AD in pediatric patients, an important secondary objective of the study is to assess the ability of baricitinib to reduce or eliminate the need for use of topical anti-inflammatory agents, the use of which is frequently a concern among parents and caregivers of pediatric AD patients.

Approximately 465 patients 2 to <18 years of age who have responded inadequately to or who are intolerant to topical therapy will be enrolled into the study, of which, approximately 25 patients will be enrolled into the Open-label PK Lead-in period (Study Period 2). The remaining patients (at least 440 patients) will be randomized at a 1:1:1:1 ratio to receive placebo QD, baricitinib low dose QD, baricitinib medium dose QD, or baricitinib high dose QD (110 patients in each treatment group with at least 320 patients 10 to <18 years old and at least 120 patients 2 to <10 years old).

The original protocol was written as a monotherapy study (including TCS washout), and the open-label PK Lead-in period (Study Period 2) will be conducted as such. Protocol amendment JAIP(a) permits the use of background low- and medium-potency TCS, and all patients participating in Study Period 3 (Double-blind treatment) will follow this for subsequent amendments including the amendment, JAIP(b).

Patients will be stratified at randomization according to disease severity (IGA 3 vs. 4) and geographic region (if the planned country allocation justifies). Definitions of geographic regions and plan for analysis by region will be described in the statistical analysis plan (SAP).

Study governance considerations are described in detail in [Appendix 3](#).

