7.2. Method of Treatment Assignment

Patients participating in the PK lead-in who meet all criteria for enrollment will receive open label baricitinib at the high dose for their age group beginning at Visit 2.

Patients not participating in the PK lead-in who meet all criteria for enrollment will be randomized in a 1:1:1:1 ratio (placebo, baricitinib low dose; baricitinib medium dose; baricitinib high dose) to double-blind treatment at Visit 2. Assignment to treatment groups will be determined by a computer-generated random sequence using an interactive web-response system (IWRS). The IWRS will be used to assign blister packs or bottles containing double-blind IP to each patient according to the Study Schedule (Section 2). Site personnel will confirm that they have located the correct blister packs or bottles by entering a confirmation number found on the blister packs or bottles into the IWRS.

Randomization will be stratified by disease severity at baseline (IGA 3 versus 4) and geographic region if the planned country allocation justifies. Definitions of geographic regions and plan for analysis by region will be described in the SAP.

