applicable. An unstructured (co)variance structure will be used to model the between- and within-patient errors. If this analysis fails to converge, other structures will be tested. The Kenward–Roger method will be used to estimate the degrees of freedom. Type III sums of squares for the least squares means (LSMs) will be used for the statistical comparison; 95% CI will also be reported. Contrasts will be set up within the model to test treatment groups at specific time points of interest. Further details on the use of MMRM will be described in the SAP.

Treatment comparisons of continuous efficacy and health outcome variables may also be made using analysis of covariance (ANCOVA) with region, disease severity, treatment group, and baseline value in the model. Type III tests for LSM will be used for statistical comparison between treatment groups. The LSM difference, standard error, p-value, and 95% CI may also be reported. The method used to handle missing data will be specified in the SAP.

Fisher’s exact test will be used for the AEs, discontinuation, and other categorical safety data for between-treatment group comparisons. Continuous vital signs, body weight, and other continuous safety variables including laboratory variables will be analyzed by an ANCOVA with treatment and baseline value in the model. Shift tables for categorical safety analyses (e.g., “high” or “low” laboratory results) will also be produced.

Missing data imputation:

1. Nonresponder imputation (NRI): All patients who discontinue the study or the study treatment at any time for any reason will be defined as nonresponders for the NRI analysis for categorical variables such as IGA 0/1 or EASI 50/75/90 after discontinuation and onward. Patients who receive rescue therapy will be analyzed as nonresponders after rescue and onward. An additional analysis will be performed that includes all available data whether rescue medication was given or not.
2. Continuous variables such as EASI and SCORAD scores will be assumed to be missing after rescue or discontinuation and then an MMRM analysis will be performed. An additional analysis will be performed that includes all available data whether rescue medication was given or not.

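### The ANCOVA for TCS-free days and TCS grams leaves out disease severity, a randomisation stratum, and region, unlike the protocol's general efficacy ANCOVA

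*Protocol*

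**What the plan says.** Protocol Section 10.3.3.2 assigns most continuous secondary measures to the mixed model for repeated measures (MMRM). For TCS-free days and grams of TCS (tube weights) it sets a separate model: "The following measures will be analyzed by an ANCOVA with treatment and baseline value in the model".

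Section 10.3.1 describes a different ANCOVA for continuous efficacy and health outcome variables. Treatment comparisons "may also be made using analysis of covariance (ANCOVA) with region, disease severity, treatment group, and baseline value in the model". For continuous safety variables the same section says they "will be analyzed by an ANCOVA with treatment and baseline value in the model", which is the form given to the TCS endpoints.

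Section 7.2 sets the allocation: "Randomization will be stratified by disease severity at baseline (IGA 3 versus 4) and geographic region if the planned country allocation justifies". Age is not named as a stratum.

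The other efficacy models are fuller. The MMRM in Section 10.3.1 reads: "The model will include treatment, age cohort, baseline severity, visit, and treatment-by-visit interaction, and treatment-by-age cohort interaction as fixed categorical effects", with region as an option. The primary logistic model in Section 10.3.3.1 contains region, severity, age, treatment and treatment-by-age.

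On the standing of topical anti-inflammatory treatment, TCS included, Section 5.1 says "an important secondary objective of the study is to assess the ability of baricitinib to reduce or eliminate the need for use". Section 4 nevertheless lists both TCS endpoints under Other Secondary, the group without multiplicity adjustment.

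**The concern.** When randomisation is stratified on a prognostic factor and the model leaves that factor out, the design removes between-stratum variation from the treatment comparison but the model leaves it in the residual. The standard error is then overstated, the interval is too wide and the test is conservative.

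Severity is a plausible predictor here. Section 7.7.2 directs TCS to affected areas until lesions are clear or almost clear, so sicker children should use more of it for longer. The TCS endpoints are also the only efficacy measures for which Section 10.3.3.2 names ANCOVA as the analysis, yet they receive the safety form of that model rather than the efficacy form. At stake are some precision on two endpoints that address a stated aim of the trial, and a needless choice between two ANCOVAs in one protocol.

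**Working it through.** **1. The models side by side**

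| Model | Disease severity | Region | Age |
|---|---|---|---|
| TCS ANCOVA (10.3.3.2) | no | no | no |
| General efficacy ANCOVA (10.3.1, optional) | yes | yes | no |
| Safety ANCOVA (10.3.1) | no | no | no |
| MMRM (10.3.1) | yes | if applicable | cohort |
| Logistic (10.3.1, 10.3.3.1) | yes | yes | yes |
| Randomisation stratum (7.2) | yes | conditional | no |

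The TCS ANCOVA and the general efficacy ANCOVA differ by exactly two terms, severity and region. They do not differ on age.

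**2. Inputs for size**

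N = 440 in four equal arms of 110, two-sided alpha 0.05 (Sections 10.1 and 10.3.1). The protocol states no effect size, standard deviation, correlation or power for the TCS endpoints, so there is no planned figure to reproduce. Let R² be the share of variance remaining after baseline that the omitted strata explain. R² is an assumption, shown from 0 to 0.20.

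**3. Formulas**

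- Inflation of the reported standard error: 1/√(1 − R²) − 1. Example: R² = 0.10 gives 1/√0.90 = 1.054.
- Actual size of a nominal 0.05 test when the omitted strata are balanced by design: 2 × [1 − Φ(1.960/√(1 − R²))]. Example: 1.960 × 1.054 = 2.066, size 0.039.
- Power when the full model has 80% and the strata are balanced: Φ(1.960 + 0.842 − 1.960/√(1 − R²)). Example: Φ(2.802 − 2.066) = Φ(0.736) = 76.9%.

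| Assumed R² | SE inflation | Actual size | Power (80% in full model) |
|---|---|---|---|
| 0 | 0% | 0.050 | 80.0% |
| 0.02 | 1.0% | 0.048 | 79.4% |
| 0.05 | 2.6% | 0.044 | 78.5% |
| 0.10 | 5.4% | 0.039 | 76.9% |
| 0.20 | 11.8% | 0.028 | 72.9% |

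**4. Simulation check**

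Settings: 4,000 trials per scenario, 440 patients, blocks of four within severity by three assumed regions, with no treatment effect. For R² = 0.05, 0.10 and 0.20 the reported standard error was 2.6%, 5.4% and 11.9% larger without the strata. The rejection rate of the reduced model was 0.038, 0.036 and 0.028. At R² = 0 the standard errors were equal. In no scenario did the reduced model reject more than 5% of the time.

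**The case against.** The strongest reply is that nothing is broken. Section 10.3.1 only permits its ANCOVA, and Section 10.3.3.2 gives a specific rule for two named measures, so an analyst knows which model to fit. That is right. The fault is an inconsistency to be reconciled, not a breach of a fixed rule.

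Four stronger readings are tempting and are not supported.

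- **That omitting age contradicts the protocol's own ANCOVA.** The ANCOVA in Section 10.3.1 has no age term, and age is not a randomisation stratum. The contrast is only with the logistic model and the MMRM.
- **That the result is biased or the error rate inflated.** Randomisation protects the comparison, and leaving out balanced strata makes the test conservative.
- **That the loss is known to be large, above all for grams because body size varies so much between ages 2 and 17.** What counts is the variance left after baseline use. Table JAIP.2 has tubes weighed out at Visit 1 and back at Visit 2, with the TCS diary running from Visit 1, so a baseline value from the same child could already carry much of body size and severity. It may do so imperfectly, because screening lasts anywhere from 8 to 35 days. The documents do not settle whether the remaining share is near zero or 20%.
- **That Section 5.1's language makes this a high-stakes analysis.** Both endpoints are Other Secondary and no stated power rests on them.

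What survives the reply is that severity is a definite stratum, a model without it is written into the protocol, and adding it costs almost nothing.

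**Conclusion.** The point holds as a consistency and efficiency matter. The stated ANCOVA for both TCS endpoints omits disease severity, a definite randomisation stratum, and region, a conditional one, while the protocol's permissive efficacy ANCOVA includes both. The consequence is conservative standard errors, by 0% to about 12% over the assumed R² range of 0 to 0.20. The direction rests on these factors predicting TCS use beyond baseline, which is plausible but not shown in the protocol; if they do not, nothing is lost. The inconsistency itself is certain from the text, while the size of the loss is not.

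**What to change.** In Section 10.3.3.2, specify the ANCOVA for both TCS endpoints with treatment, baseline value, disease severity (IGA 3 or 4) and, if randomisation is stratified by it, region. That brings it into line with Section 10.3.1. Age cohort may be added so that these endpoints match the logistic model and the MMRM; this is for consistency across models, not to resolve a contradiction.

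Keep grams over 16 weeks as the endpoint. Expressing use per kilogram or per square metre would change the quantity named in Section 4 and is not needed to reconcile the models.

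The cost is a wording change, settled before unblinding. The covariates are already collected, and the model spends a few degrees of freedom out of about 440.
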